ISRCTN	International Standard Randomised Controlled Trial Number
LHB	Local Health Board
MREC	Multi-Centre Research Ethics Committee
PI	Principal Investigator
PIAG	Patient Information Advisory Group
PIS	Patient Information Sheet
QL (QoL)	Quality of Life
R&D	Research and Development
RCT	Randomized Controlled Trial
SAE	Serious Adverse Event
SEWTU	South East Wales Trials Unit
SMF	Study Master File
SMG	Study Management Group
SSC	Study Steering Committee
SSI	Site Specific Information
SUSAR	Suspected Unexpected Serious Adverse Reactions

Definitions:

Antibiotic Associated Diarrhoea (AAD) is defined as "three or more loose stools in a 24 hour period during or within 8 weeks of stopping oral or parenteral antibiotic treatment following normal stool consistency on the day commencing the antibiotic" according to the Bristol Stool Form Scale" (adapted KW Heaton, University of Bristol).

C. difficile **Associated Diarrhoea** (CDAD) is defined as "Diarrhoea not attributable to any other cause which occurs at the same time as a positive toxin assay (with or without a positive *C. difficile* culture) or endoscopic evidence of pseudomembranous colitis."

Probiotics

Probiotics are dietary supplements containing a mono- or mixed culture of live micro organisms such as bacteria or yeasts which, when administered in adequate amounts, confer a health benefit on the host by improving the properties of the indigenous microflora [1]. Probiotics can be purchased over the counter in pharmacies and supermarkets and are taken by the public on a daily basis

Care Homes

Nursing Home Residential Home Dual Registered Care Home

1. Study summary & schema

1.1 Study Summary

PAAD is a two Stage study.

This protocol is for Stage 1 *only***: Establishing the platform.Stage 1:** There is currently a lack of evidence regarding; 1) the frequency of antibiotic prescribing and type of antibiotic prescribed in care homes in the UK and, 2) how often diarrhoea occurs associated with taking antibiotics, and its severity.

Nine care homes in South Wales and the care home service users (residents) will be recruited for Stage 1. The main part of Stage 1 is a 12 month prospective **observational study** that aims to collect data (e.g. amount and type of antibiotics prescribed episodes of Antibiotic Associated Diarrhoea (AAD) and *Clostridium difficile*-associated diarrhoea (CDAD) and outcome, in a purposive sample of care homes. Additionally, there will be 3 sub-studies within Stage 1.

Main Observational Study

Data regarding indication for prescribing, type of antibiotic, dose, route of administration and duration of antibiotic will be collected each time a participating service user is prescribed antibiotics by their GP. Should a service user who is prescribed antibiotics develop diarrhoea, either during, or within, eight weeks of stopping the antibiotic(s), a stool sample will be collected and sent, as per routine procedure, to the local lab for standard microbiological stool analysis including *C. difficile* analysis as well as to the central lab to test for *C. difficile* and screening for carriage of antibiotic resistant bacteria. A stool chart will be completed for the duration of antibiotic treatment and for an additional eight weeks after the antibiotic course is complete.

Sub-Studies

Sub study 1: C. difficile Prevalence

A baseline stool sample will be collected from care home service users to assess *C. difficile* prevalence in the Care Homes. Data about previous antibiotic use by the service user, for a 3 month period before entry to this sub-study will also be collected.

Sub Study 2 Qualitative Observational Study of Care Home Routines

To account for the known difficulties in conducting research in this setting, we plan to carry out observations of daily care routines within the care homes to gain a greater understanding of how a sample of care homes operate and how this might impact upon a Randomised Controlled Trial to determine the effectiveness of probiotics given alongside antibiotics in reducing Antibiotic Associated Diarrhoea.

In order to achieve this, we plan to observe a range of daily care routines and features of care homes participating in PAAD stage 1, in order to inform the design of PAAD stage 2.

Sub study 3: Qualitative Study

1) Qualitative interviews will be conducted with service users capable of consent, and 2) focus groups will be conducted with family members and care home staff discussing issues around consent and assent in care home residents. 3) Additional interviews with GPs regarding these issues will also be conducted.

The focus groups and interviews will also take into account issues from sub study 2 (above). For more details on Sub-Study 3, see Section 17.3

[figure not shown]
Sub study 4 - Measuring quality of life by proxy in care homes: An exploration of differences between proxy types (EQ-5D by Proxy)

The EQ-5D questionnaire is a well-established method of assessing Health Related Quality of Life (HRQol (www.euroqol.org) and is preferred by the National Institute for Health and Clinical Excellence for use in cost utility studies (NICE, 2009). However, there are problems associated with obtaining responses to HRQoL questions from those who are restricted in their ability to make judgements. This sub- study is testing the hypothesis that there is an inverse relationship between agreement in subject/proxy EQ-5D scores and subject's level of cognitive competence. If results support this hypothesis, then a minimum level of cognitive competence will be identified for which EQ-5D data should be collected by proxy. The study will also explore whether a combination of professional and friend/relative proxies would be preferable to either proxy alone.

In summary, Stage 1 will identify the scale of the AAD problem in care homes, provide reliable incidence data and confirm the basis of our sample size calculation for the randomised controlled trial (RCT) in Stage 2. Stage 1 will also allow us to pilot the trial procedures and materials required for a RCT in Stage 2. If Stage 1 indicates that AAD is a rare, unimportant problem, then, based on explicit stopping rules, we will not progress to Stage 2.

Stage 2 (For information only): If, during Stage 1, the *a priori* specified incidence threshold is met, Stage 2 will be conducted. Stage 2 is a randomised controlled trial to assess whether AAD is prevented or ameliorated in care home service users receiving antibiotics by the administration of a probiotic along side the antibiotic. Based on limited published literature, we estimate that this aspect of the study, Stage 2, will involve 450 service users in 50 care homes in Wales and the South West. However, Stage 1 is being done partly because the evidence to support this sample size calculation is inadequate. At any point during a one year period, if the residents' doctor considers them to have developed an infection that requires antibiotic treatment, they will be randomly allocated to receive either a course of probiotic or an identical placebo together with their prescribed antibiotic.

Main Observational Study

2 Introduction

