7.4 Screening logs

An anonymous screening log of all ineligible and eligible but not consented/not approached Service Users will be kept at each centre so that any bias from differential recruitment will be detected. The screening log should be sent to the PAAD Trial Manager when all service users have been approached to join the study and those willing to consent have consented.

8 Study procedures

Before any study related procedures are undertaken, the service user's or service user representative's written informed consent will be obtained. Consent to participate in the main observational study for 12 months and consent for the prevalence sub-study 1 will be taken at initial recruitment of service users. All data forms should be as complete as possible and every effort should be made to collect the data at the desired time points for the appropriate participant.

Table 1 details the PAAD Case Report Form (CRF), time point for data collection and who has overall responsibility for collecting the data. The original CRF will be sent to the PAAD Trial Manager (see contacts for address details) and a copy kept at the care home. The PAAD Study research nurse or NISCHR research nurses/officers, where required, will also able to collect any of the data listed below.

CRF	Time point	Collected by
Eligibility/recruitment CRF	Immediately post consent/assent	Care home staff
Baseline CRF	Immediately post consent/assent	Care home staff /Research Nurse
Prevalence Study Stool CRF	Within one week from consent	Care home staff /Research Nurse
Antibiotic CRF	Day of commencement of antibiotic treatment until duration end date	Care home staff /Research Nurse
Stool Chart CRF	Day of commencement of antibiotic treatment, every day for duration of antibiotic + 8 weeks	Care home staff /Research Nurse
Loose Stool CRF	When participant develops diarrhoea.	Care home staff /Research Nurse
Withdrawal CRF	Following a withdrawal	Care home staff
SAE CRF	Following any adverse event	Care home staff

Table 1 Data collection table

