8.1 Body measurements

At baseline, at the time of being prescribed antibiotics and at the end of the eight week follow up, an assessment of body composition/nutrition status (MUST score) will be taken. Where it is not possible to weigh a service home user the Mid Upper Arm Circumference (MUAC) will be done.

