11.1 Sampling frame and sample size

We will recruit care homes (residential & nursing) within South East Wales. This will be a purposive sample, in that it will ensure contrasting care homes are recruited to include residential, nursing and dual care. The sampling frame will be based on the following criteria:

1) Predominant type of care - residential/nursing/dual

Care homes will be split into three strata, based on the type of care home: nursing, residential and dual. Three from each care homes from each stratum will be recruited to total nine care homes. Recruiting three randomly selected care homes from each of the different strata will allow some insight into the amount of variability between and within different types of care homes (both in terms of the homes themselves and their residents).

Nine care homes will give a sample of approximately 270 Service users. From previous literature, we estimate 40% of care home users are likely to be prescribed antibiotics over a 12 month period. This will enable us to fit a 95% confidence interval to an AAD rate of 25% of +/- 10%. One family focus group around the issues of consent and assent will be conducted in each care home. Additional interviews will be conducted with study participants capable of consent.

11.2 Timing and criteria to justify Stage 2

We will evaluate three months of data collection regarding antibiotic use in nine care homes, together with two additional months of data for AAD. This analysis will provide us with numbers of asymptomatic carriers of *C.diff*, and provide an estimate of numbers of antibiotic prescriptions and AAD including CDAD. The duration and severity of the AAD will also be known.

This data, along with participant consent and follow-up rates, will be used to justify proceeding to a randomised trial in this setting (i.e. Stage 2).

Feasibility components of Stage 1

The feasibility components of Stage 1 are designed to: Optimise procedures for setting up care homes sites to be able to undertake a clinical trial of an Investigational Medicinal Product (CTIMP); Optimise informed consent process in a vulnerable population;

Estimate rate of agreement to participate;

Optimise rate of sampling for follow-up.

To identify the minimum level of cognitive competence below which EQ-5D data should be collected by proxy.

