12.1 Main analysis

The primary objectives for the main observational study are:

1. To fit a 95% confidence interval around the estimate annual AAD rate which we currently estimate to be 25% based on available evidence.

The secondary objectives for the main observational study are;

1. To describe the type, dose and treatment regimes of the antibiotics taken by service users. We will tabulate each type of antibiotic against the frequency and severity of AAD;

2. To tabulate summary statistics of the incidence of *C. difficile*, the number of repeat cases of diarrhoea, duration from onset and severity.

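### Stool charting ends on the same day as the AAD onset window, so episodes still open that day have a truncated charted duration

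*Protocol*

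**What the plan says.** - **Onset.** The Definitions in the glossary count AAD as "three or more loose stools in a 24 hour period during or within 8 weeks of stopping oral or parenteral antibiotic treatment".
- **Charting.** Section 1.1 says: "A stool chart will be completed for the duration of antibiotic treatment and for an additional eight weeks after the antibiotic course is complete". Table 1 in section 8 repeats the window for the Stool Chart CRF: "every day for duration of antibiotic + 8 weeks".
- **Extension.** Section 8.4 restarts the antibiotic CRF and the eight-week chart when antibiotics are restarted or newly prescribed during follow-up. No section extends charting because diarrhoea is still present.
- **Other records.** Table 1 gives the trigger for the Loose Stool CRF as "When participant develops diarrhoea". It gives no content and no end point for that form. Section 8.6 seeks consent to extract data from care home, primary and secondary care records.
- **Nutritional measure.** Section 10.1 lists MUST/MUAC as the AAD and CDAD outcome. Section 8.1 fixes the last one: "at the end of the eight week follow up, an assessment of body composition/nutrition status (MUST score) will be taken".
- **What is promised.** Section 11.2, on the data used to justify Stage 2, says: "The duration and severity of the AAD will also be known". Section 12.1 plans summary statistics that include "the number of repeat cases of diarrhoea, duration from onset and severity".

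**The concern.** A single end date serves two purposes. It closes the period in which an AAD episode can start, and it closes the daily observation of any episode already under way. A resident whose diarrhoea starts on day 55 after the course, and who completes every planned day of charting, contributes at most two charted days of that episode (days 55 and 56), however long it lasts.

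This truncation can only shorten a charted duration, and for a given onset pattern it falls most on the longest episodes. Duration is among the items that section 11.2 brings to the judgement on Stage 2, and it is a secondary tabulation in section 12.1. Stage 1 also pilots procedures for Stage 2, which asks whether AAD is prevented or ameliorated, so the same chart rule could carry over into the trial. An analysis can flag a missing end date as censored, but it cannot recover it. The rule therefore has to be set where data collection is set, in the protocol.

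**Working it through.** The plan states no figure for this point, so there is none to reproduce. The check has two parts.

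**1. The windows side by side**

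- Last day on which AAD can begin: day 56 after the course (Definitions).
- Last chart day: day 56 after the course (1.1, Table 1).
- Trigger for further charting: restarted or new antibiotics only (8.4).
- Section that assigns an end date of diarrhoea to the Loose Stool CRF or to record extraction: none.

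An episode that begins k days before the chart ends therefore has at most about k days charted. One that resolves before day 56 is fully charted.

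**2. How many episodes are cut**

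Inputs from section 11.1: 270 service users, 40% prescribed antibiotics in 12 months, AAD rate 25%. Expected cases, with the 25% read as a share of antibiotic recipients: 270 × 0.40 × 0.25 = 27.

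Assumptions, none given in the documents: a course of 7 days, one episode per case, episode length d of 3 to 14 days, and two patterns of onset. Window W = 7 + 56 = 63 days.

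*Uniform onset.* The share cut is d/W. A cut episode loses d/2 on average, so mean duration is understated by the fraction d/(2W) = d/126.

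| d (days) | share cut | of 27 | mean understated by |
|---|---|---|---|
| 3 | 3/63 = 4.8% | 1.3 | 2.4% |
| 7 | 7/63 = 11.1% | 3.0 | 5.6% |
| 14 | 14/63 = 22.2% | 6.0 | 11.1% |

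Course length matters little. For d = 7 the share is 7/61 = 11.5% with a 5-day course and 7/70 = 10.0% with a 14-day course.

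*Front-loaded onset.* Let onset follow an exponential with scale m days, truncated at W, so F(t) = (1 − e^(−t/m)) / (1 − e^(−W/m)). The share cut is 1 − F(W − d) for a fixed duration d. The last two columns let duration vary exponentially with mean d.

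| d (days) | m = 10, fixed | m = 21, fixed | m = 10, exponential | m = 21, exponential |
|---|---|---|---|---|
| 3 | 0.06% | 0.8% | 0.08% | 0.9% |
| 7 | 0.19% | 2.1% | 0.40% | 2.6% |
| 14 | 0.56% | 5.0% | 3.3% | 8.1% |

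For episodes up to 7 days the largest value is 2.6%, and 27 × 0.026 = 0.7 of a case. For 14-day episodes the largest is 8.1%, and 27 × 0.081 = 2.2 cases.

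**3. The Stage 2 evaluation**

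Section 11.2 uses three months of antibiotic data "together with two additional months of data for AAD". If prescribing is even over the year (assumption), 27 × 3/12 = 6.75 cases are in view. Under uniform onset the number cut is then 6.75 × 4.8% = 0.3, 6.75 × 11.1% = 0.75 or 6.75 × 22.2% = 1.5 for d = 3, 7 or 14.

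Two months is about 61 days, against 63 for a 7-day course plus eight weeks. For courses begun at the very end of month three, the data cut can fall slightly before even the planned chart is complete.

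**The case against.** The strongest case on the other side has five parts.

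- **Few episodes are affected.** A reader might infer that late-onset episodes are never followed to resolution. The documents do not support that. An episode starting on day 40 and ending on day 50 is fully charted, and a new antibiotic course restarts the chart. This stands, and the point is limited to episodes open on day 56.
- **The chart may not be the only source.** The content of the Loose Stool CRF is not shown, and records may be extracted. This stands in part: either could hold an end date, but the protocol assigns that task to neither.
- **Serious courses may still be recorded.** A reader might infer that progression to severe illness would go unseen in late cases. SAE reporting (sections 9.1 and 9.2) covers death, life-threatening events and hospitalisation, with no eight-week limit stated, and results of diarrhoeal samples go to the GP and the trials unit. So that inference fails, although ordinary duration is not an SAE item.
- **Severity is not shown to be biased.** A reader might extend the downward bias from duration to severity. The protocol gives no severity measure from which such a bias could be calculated, and the arithmetic covers duration only.
- **The consequence is limited.** The primary objective is AAD incidence, and onset is observed over the whole definition window. Section 1.1 ties Stage 2 to an incidence threshold, and section 11.2 sets no criterion on duration. Handling of censored durations may also sit in a SAP that is not shown. All of this stands, but a SAP cannot supply chart days that were never collected.

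The fixed-time MUST/MUAC is also defensible, because it keeps the timing comparable between residents. That it misses the effect of a late episode is possible but not shown.

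**Conclusion.** The point holds in a limited form. The protocol ends onset eligibility and daily charting on the same day and has no rule for continuing an open episode, so the statement that AAD duration will be known is too strong for those episodes. Following the rule as written gives a charted duration that is biased downward, and no other source is named to correct it.

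The size depends on assumptions about course length, episode length and onset timing that the documents do not give. It runs from fewer than 1 of 27 expected cases (front-loaded onset, episodes up to 7 days) to about 6 of 27 (uniform onset, 14-day episodes). At the Stage 2 evaluation it is about 1.5 cases at most under the same assumptions. The incidence estimate is untouched. This is a modest flaw in a secondary outcome, worth correcting because the correction is specific and cheap.

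**What to change.** 1. In section 1.1, section 8.3 and Table 1, state that the 8-week limit applies to the onset of AAD.
2. In the same places, state that for any episode open on the last chart day the Stool Chart CRF continues until a defined resolution, death or leaving the home. Resolution could be, for example, a set number of consecutive days on which the three-loose-stools criterion is not met; the sponsor should fix that number.
3. In section 12.1, report episodes still open at the data cut or at study closure as censored for duration. In section 11.2, qualify the statement that duration will be known in the same way.
4. Keep the fixed-time MUST/MUAC. A repeat at resolution is optional.

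The cost is a few extra chart days for a small number of residents and a change of wording in a few places. No new staff or procedure is needed, and treatment is not affected.

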2.1 Background

2.1.1 Antibiotic Associated Diarrhoea (AAD)

Antibiotic treatment disrupts the normal flora of the gut, sometimes causing diarrhoea. While any antibiotic can cause AAD, clindamycin, cephalosporins, aminopenicillins and more recently fluoroquinolones, have been identified as more likely to cause AAD, particularly in hospitalised patients. Older patients with frequent hospitalisations and high co-morbidity are at greatest risk of developing AAD. Little is known either about the frequency and type of antibiotics prescribed in care homes, or about the incidence and aetiology of AAD in this setting. AAD varies in seasonal incidence being more common in winter, and has been shown to occur in up to 39% of hospitalised patients receiving antibiotics [2]. Little is known about the incidence of AAD in primary care or care homes.

2.1.2 Clostridium difficile (C. difficile)

Clostridium difficile is a Gram-positive, spore-forming bacillus. It was first described in 1935 and by 1978 it had been identified as the pathogen responsible for pseudomembranous colitis[3]. It has more recently been highlighted as a potentially serious threat to hospitalised patients and care home residents, causing high levels of morbidity and, in some cases, death [4, 5]. The spores of *C. difficile* can survive for lengthy periods in the environment and gut; therefore, there is a high risk of cross infection, either through direct patient-to-patient contact, via healthcare staff, or via a contaminated environment. Routinely collected voluntary surveillance Health Protection Agency (HPA) data (2009) show that though the incidence rate of *C. difficile* per population is decreasing since 2008, the incidence rate is still high in England Wales and Northern Ireland being 50, 59 and 55 samples per 100,000 population respectively. Around 77% of all reported cases were in the 65 years and over age group.

2.1.3 C. difficile associated diarrhoea (CDAD)

C. difficile associated diarrhoea (CDAD) is the most commonly identified cause of AAD, and most cases of pseudomembranous colitis. CDAD typically occurs in hospitals (including community hospitals) but also occurs in care homes and primary care settings (DH website). CDAD occurs most often as a consequence of disruption of the indigenous protective colonic microflora following broad-spectrum antibiotic treatment. *C. difficile* accounts for 20-30% of AAD [6], although some estimates are more conservative [7]. In the majority of patients,

full recovery is usual, although particularly elderly and frail patients may suffer loss of dignity, become seriously ill with dehydration as a consequence of the diarrhoea, and may progress to develop life threatening pseudomembranous colitis.

Exposure to antibiotics within the previous 2 months is the most important risk factor for developing CDAD [8]. other well recognised risk factors include age (hospital patients aged over 65 years are four times more likely to develop CDAD compared to younger, general medicine patients: 73.6 vs. 16 per 1000 admissions), hospitalisation, severity of underlying illness, nasogastric tube and use of proton pump inhibitors or H_2 agonists [9-11].

